1.2.5 Randomisation and blinding

This is an open-label study and so there is no blinding.

Randomisation will be conducted through a validated online system (sealedenvelope.com) provided through the LCTU. Eligible participants will be randomly assigned at their Baseline Visit (Day 0) in a 2:1 ratio to participate in a Tier 3 service with:

- 1) *Targeted prescribing pathway - The use of once daily subcutaneous injections of Liraglutide (if they meet the pre-specified criteria), starting at a dose of 0.6 mg with gradual and pre-specified increments to 3.0mg*
or
- 2) *Control Group - No additional treatment.*

A 2:1 ratio will be used so that a sufficient number of responders will be available for responder analyses. Randomisation will be stratified by centre and BMI ($\geq 45\text{kg}/\text{m}^2$; $< 45\text{kg}/\text{m}^2$).

Participants will be informed of their randomisation assignment during the Baseline Visit. A letter will be sent to the participant's GP notifying them of their patient's participation in the study. Both the participant and their GP will have the randomisation assignment confirmed by letter.

1.3 Visit schedule

The original visit schedule was as follows:

- Screening and Consent Visit (Day -42 to -1)
- Data Collection Visits – All participants
 - Baseline Visit (Day 0) - including randomization and treatment initiation for participants randomized to the intervention arm
 - Week 52
 - Week 104

- Clinical Review (safety and retention) Visits – All participants
 - Weeks 2, 4, 8, 12, 16, 20, 32, 40, and 78
- Additional Clinical Review (safety and retention) Visits for LIRA 3mg group
 - Weeks 65 and 91

In response to the COVID-19 global pandemic, an interim time point for the quality-of-life questionnaires was added. The following questionnaires were sent out to all participants during the COVID-19 pandemic:

- Health Services and Resources Use Questionnaire (HSRUQ)
- Treatment Satisfaction Questionnaire for Medication (TSQM)
- European Quality of Life -5 Dimensions (EQ-5D)
- Impact of Weight on Quality of Life-Lite (IWQOL-Lite)
- International Physical Activity Questionnaire-Long (IPAQ-Long)
- Patient Health Questionnaire-9 (PHQ-9).

Where possible, the week 52 visit continued to be scheduled within the \pm 14 days study visit window, however to aid retention and to help maximise data collection for the study primary end point, the week 52 visit window could be extended to \pm 3 months. Where it was not possible to conduct a week 52 visit (e.g., because of COVID-19 restrictions in place at the time), weight data were obtained from the participant's hospital, GP or health record instead where a measurement was available within a window of +/- 12 weeks from the scheduled week 52 visit to ensure that the primary outcome was as complete as possible.

2 Outcomes and other variables

2.1 Primary Endpoint

2.1.1 Definition and Derivation of Primary Endpoint

Binary outcome indicating whether weight loss of $\geq 15\%$ was achieved at 52 weeks.

Percentage weight loss at 52 weeks will be derived for each participant using the following formula:

$$\frac{(weight_{baseline\ visit} - weight_{52\ week\ visit})}{weight_{baseline\ visit}} \times 100$$

The primary endpoint will then be coded as 1 if the percentage weight loss at 52 weeks is $\geq 15\%$, and as 0 otherwise.

As stated in section 1.3 where weight is not available from week 52 visit, weight from routinely collected data will be used instead if possible.

2.1.2 Hypothesis to be investigated

The primary hypothesis is that a targeted prescribing pathway using LIRA 3mg according to a pre-specified protocol in combination with standard care provided in Tier 3 services will be associated with more participants achieving weight loss of $\geq 15\%$ at 1 year than receiving standard care provided in Tier 3 services alone.

2.2 Secondary Endpoints

2.2.1 Definition and Derivation of Secondary Endpoints

Endpoint	Time point (weeks)	Endpoint derivation
Anthropometric endpoint		
Absolute change in weight (kg) from baseline	16, 32, 52, 104	Follow-up weight – baseline weight
Relative change in weight (%) from baseline	16, 32, 52, 104	(Baseline weight – follow-up weight)/baseline weight * 100
Weight loss of $\geq 5\%$, $\geq 10\%$ and $\geq 15\%$	16, 32, 52, 104	Binary indicator of 1 if relative change in weight from baseline is $\geq 5\%$ loss (or $\geq 10\%$ or $\geq 15\%$, respectively), 0 otherwise
Maintenance of weight loss of $\geq 15\%$ among those who lost $\geq 15\%$ at 52 weeks	104	Binary indicator of 1 if relative change in weight from baseline is $\geq 15\%$ loss, 0 otherwise, only calculated for those who lost $\geq 15\%$ of baseline weight at 52 weeks.
Absolute change in BMI (kg/m^2) from baseline	52, 104	Follow-up BMI – baseline BMI
Absolute change in waist circumference (cm) from baseline	52, 104	Follow-up waist circumference – baseline waist circumference
Obesity-related co-morbidities and their treatments (General)		
Score on King's College Obesity Staging System assessment	52, 104	Scored as per Staging System (Appendix 1) as Stage 0 (normal health), 1 (at risk of disease), 2 (established disease), 3 (advanced disease) with baseline values also presented
Quality of life (EQ5D) – Descriptive System	52, 104	Scored as per https://www.unmc.edu/centric/_documents/EQ-5D-5L.pdf with change from baseline value analysed separately for each dimension
Quality of life (EQ5D) – Visual Analogue Scale	52, 104	Scored as per https://www.unmc.edu/centric/_documents/EQ-5D-5L.pdf with change from baseline value analysed
Impact of Weight on Quality of Life-Lite (IWQOL-Lite)	52, 104	Transformed total score on scale of 0-100 scored as per https://www.qualityoflifeconsulting.com/iwgol-lite.html with change from baseline

		value analysed
Patient Health Questionnaire-9 (PHQ-9)	52, 104	Scored as per Appendix 2 as minimal depression, mild depression, moderate depression, moderately severe depression, severe depression with baseline values also presented
Patient Health Questionnaire-9 (PHQ-9)	52, 104	Total score generated as per Appendix 2 with change from baseline analysed
Obesity-related co-morbidities and their treatments (Obstructive Sleep Apnoea; OSA)		
Epworth Sleepiness Scale	52, 104	Scored as per Appendix 3 as binary outcome for possible OSA or not with baseline values also presented
Epworth Sleepiness Scale	52, 104	Total score generated as per Appendix 3 with change from baseline analysed
Stop Bang questionnaire	52, 104	Scored as per Appendix 4 as no OSA (0-2), possible OSA (3-4), likely OSA (5-8) with baseline values also presented
Stop Bang questionnaire	52, 104	Total score generated as per Appendix 4 with change from baseline analysed
On CPAP	52, 104	Binary indicator of 1 if participant is on CPAP, 0 otherwise with baseline values also presented
Apnoea Hypopnoea Index for participants with sleep apnoea who cannot tolerate CPAP or for participants on fixed pressures CPAP	52, 104	Recorded as an integer in MACRO (AHI = sum of the number of apneas (pauses in breathing) plus the number of hypopneas (periods of shallow breathing) occurring on average, each hour.)
Oxygen desaturation index for participants with sleep apnoea who cannot tolerate CPAP or for participants on fixed pressures CPAP	52, 104	Recorded as integer in MACRO (The average number of desaturation episodes per hour can be measured using PSG and is called the oxygen desaturation index (ODI))
Obesity-related co-morbidities and their treatments (Prediabetes/Diabetes)		
Change in HbA1C from baseline (mmol/mol)	52, 104	Follow-up HbA1c – baseline HbA1c. Will be calculated for each Glycaemic Status separately as well as for all individuals, see Appendix 8 for Glycaemic Status definitions.

Change in HbA1C from baseline (%)	52, 104	Follow-up HbA1c – baseline HbA1c Will be calculated for each baseline Glycaemic Status separately as well as for all individuals, see Appendix 8 for Glycaemic Status definitions)
Glycaemic Status	52, 104	Individuals are classified as having Diabetes remission, Diabetes, Pre-diabetes or Normoglycaemia. The Glycaemic Statuses will be summarised overall as well as for each baseline Glycaemic Status separately. Appendix 8 has the definitions of Glycaemic Status at baseline and follow-up.
Number of agents for diabetes	52, 104	Change from baseline in the total number of medications taken for diabetes defined as medications in any of the following classes: metformin, sulphonylurea, thiazolidinedione, SGLT-2, GLP-1, and insulin.
Proportion of those with diabetes at baseline with HbA1C<7.0%	52, 104	From HbA1c measurement, a binary indicator will be derived, being 1 if participant achieves the target and 0 if they do not.
Proportion of those with diabetes at baseline with HbA1C<6.5%	52, 104	From HbA1c measurement, a binary indicator will be derived, being 1 if participant achieves the target and 0 if they do not.
Change in Albumin-Creatinine Ratio (ACR; mg/mmol) from baseline for participants with diabetes, prediabetes, or hypertension	52, 104	Follow-up ACR – baseline ACR, only for participants defined as having diabetes, prediabetes, or hypertension
Obesity-related co-morbidities and their treatments (Hypertension)		

Systolic blood pressure (mmHg)^b	52, 104	Follow-up systolic blood pressure – baseline systolic blood pressure
Diastolic blood pressure (mmHg)^b	52, 104	Follow-up diastolic blood pressure – baseline diastolic blood pressure
Hypertension	52, 104	Binary indicator of 1 if participant is on antihypertensive medications or systolic blood pressure > 140 mmHg ^c , 0 otherwise with baseline values also presented
Number of agents for hypertension	52, 104	Change from baseline in total number of medications taken for hypertension defined as medications in any of the following classes: ACE-inhibitors, calcium channel blockers, thiazide diuretics, alpha-blockers, and beta-blockers.
Obesity-related co-morbidities and their treatments (Dyslipidaemia)		
LDL cholesterol (mmol/L)	52, 104	Follow-up LDL cholesterol – baseline LDL cholesterol
HDL cholesterol (mmol/L)	52, 104	Follow-up HDL cholesterol – baseline HDL cholesterol
Total cholesterol (mmol/L)	52, 104	Follow-up total cholesterol – baseline total cholesterol
Triglycerides (mmol/L)	52, 104	Follow-up triglycerides – baseline triglycerides
Number of agents for dyslipidaemia	52, 104	Change from baseline in total number of medications taken for dyslipidaemia defined as medications in any of the following classes: statins, fibrates, and ezetimibe.
Number of participants referred for other obesity intervention		
Referred to Tier 4 for bariatric surgery	104	Binary indicator of 1 if participant was referred to Tier 4 for bariatric surgery over 104 week period, 0 otherwise
Treatment satisfaction		
Treatment	Satisfaction	Questionnaire for Medication (TSQM)
	52, 104	Change from baseline in TSQM scale score. Scored as per version II (detailed in Appendix B on vhe.066.fm (iqvia.com)).
Safety/adverse events		
Gastrointestinal symptoms	52, 104	Binary indicator of 1 if participant experienced any nausea or vomiting in study up until the time point of interest (captured in the expected AEs), 0 otherwise
Overall hypoglycaemia rate – ADA definition	52, 104	Hypoglycaemia events will be defined as per Appendix 5 for people without

		diabetes and as per the ADA definition in Appendix 5 for people with diabetes. Hypoglycaemia rate will be calculated per participant as total number of hypoglycaemia events divided by the total follow-up time.
Overall hypoglycaemia rate – Novo Nordisk	52, 104	Hypoglycaemia events will be defined as per Appendix 5 for people without diabetes and as per the Novo Nordisk definition in Appendix 5 for people with diabetes. Hypoglycaemia rate will be calculated per participant as total number of hypoglycaemia events divided by the total follow-up time.
AEs	Continual	Defined as in protocol with MEDRA coding used to classify AEs into System Organ Classes
SAEs	52, 104	Defined as in protocol with MEDRA coding used to classify SAEs into System Organ Classes
Rates of severe hypoglycaemia	52, 104	Calculated per participant as total number of severe hypoglycaemia events divided by the total follow-up time, where severe hypoglycaemia is defined as hypoglycaemic episodes requiring the assistance of another person to actively administer carbohydrate, glucagon, or other resuscitative actions (i.e., 'severe hypoglycaemic episodes')
Change in heart rate from baseline (beats per minute)	52, 104	Follow-up heart rate – baseline heart rate
Compliance of patient with the treatment		
Compliant with Tier 3 service (completers)	52, 104	Binary indicator of 1 if participant is compliant, 0 otherwise (defined in study database)
Stopped treatment with LIRA 3mg because of adverse effects	52, 104	Binary indicator of 1 if participant stopped treatment with LIRA 3mg because of adverse effects*, 0 otherwise. Only defined for participants in intervention arm who were currently eligible for LIRA 3mg treatment. * This includes main reason of 'adverse event' or 'unable to tolerate drug'.
The adherence of participants with the LIRA	52, 104	Participants will be defined as treatment compliant if they self-administer at least 70% of planned doses. Binary indicator of 1 if participant is compliant, 0 otherwise.

3mg (monitored through specific questionnaire and return of used pens)		Given the change in visits as a result of COVID-19 to allow face-to-face, this will be defined using the questionnaire answers as detailed in Appendix 7. Only defined for participants in intervention arm who were currently eligible for LIRA 3mg treatment.
Stopped LIRA 3mg	16, 32, 52	Binary indicator of 1 if participant stopped treatment with LIRA 3mg at time-point (i.e., due to stopping rules or side effects), 0 otherwise. Only defined for participants in intervention arm who were on LIRA 3mg treatment at the previous time-point.
Completed 52 weeks of the Tier 3 service programme despite stopping LIRA 3mg at 16 weeks	52	Binary indicator of 1 if participant completed 52 weeks of the Tier 3 service programme despite stopping LIRA 3mg at 16 weeks, 0 otherwise. Only defined for participants in intervention arm who stopped LIRA 3mg treatment at 16 weeks.
Completed 52 weeks of Tier 3 service programme despite stopping LIRA 3mg at 32 weeks	52	Binary indicator of 1 if participant completed 52 weeks of the Tier 3 service programme despite stopping LIRA 3mg at 32 weeks, 0 otherwise. Only defined for participants in intervention arm who stopped LIRA 3mg treatment at 32 weeks.
Started on anti-obesity drugs	52, 104	Binary indicator of 1 if participant started on anti-obesity drugs other than LIRA 3mg, 0 otherwise. Defined as a concomitant medication listing of Orlistat.
Physical activity assessment		
International physical activity questionnaire (IPAQ- Long Form; MET-minutes/week)	52, 104	Total MET-minutes/week calculated in line with Appendix 6 and then change from baseline calculated.

^a Glucose lowering medications are defined as metformin, a sulphonylurea, a thiazolidinedione, or a SGLT-2.

^b These are also considered safety outcomes.

^c On the CRF, hypertension is a yes/no tick box with the following wording: "Hypertension treated (antihypertensives with or without diagnosis) or untreated (systolic blood pressure >140 mmHG at two consecutive visits to Tier 3 clinic)." If a definition of anti-hypertensive medications is required for the derivation of any variables then the following medication should be considered as anti-hypertensive: ACE-inhibitors, calcium channel blockers, thiazide diuretics, alpha-blockers (e.g., doxazosin) and beta-blockers.

N.B. CPAP compliance (hours/days) was listed as a secondary outcome in the protocol but will not be reported as it hasn't been captured in the database.

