After 32 weeks (\pm 14 days) on the medication, only those participants who have lost $\geq 10\%$ of their baseline weight and are still on treatment with LIRA 3mg will be offered another 20 weeks on LIRA 3mg. Participants who have not met this weight loss target will have their LIRA 3mg treatment stopped but will still continue in the targeted prescribing pathway but will receive standard care only during the remainder of the study.

3rd stopping rule: After the first year of treatment (week 52; \pm 14 days), only those participants who have lost $\geq 15\%$ of their baseline weight and are still on treatment with LIRA 3mg will be offered another 52 weeks on LIRA 3mg. Participants who have not met this weight loss target will have their

LIRA 3mg treatment stopped and will still continue in the targeted prescribing pathway but will receive standard care only during the remainder of the study.

Participants who fail to reach the pre-defined weight-loss targets to continue LIRA 3mg treatment, or who choose to stop receiving LIRA 3mg, will continue to be offered the standard care provided by the Tier 3 service. These participants will still attend the Clinical Review Visits but not the additional visits for participants who are still on LIRA 3mg (e.g. Weeks 65 & 91) because these visits will not be relevant to them; visits at Weeks 65 and 91 are intended to provide a new prescription of LIRA 3mg and to discuss adherence and any side effects; see Appendices 2 & 3).

Participants will remain routinely in the Tier 3 service in-line with NICE guidance throughout the duration of the research study. Participants may be offered treatment options within the duration of the study, including bariatric surgery, as per NICE guidance and according to the decision of the local Tier 3 Multidisciplinary Team. Participants who have undergone bariatric surgery after randomisation will only be included in the intention to treat (ITT) analysis. This decision was made because the proportion of participants undergoing bariatric surgery is likely to be unbalanced between the treatment groups (i.e. more participants in the control group are expected to have bariatric surgery than in the targeted prescribing pathway treatment group), and thus weight loss in these individuals could unduly influence the study results. Participants who have been prescribed and start anti-obesity medication (such as Orlistat) will be ineligible for LIRA 3mg treatment.

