3.3.1 Complete Cases Population

The complete cases population is defined as all randomised participants who have data available for the outcome being analysed, according to the study group to which they were randomised at baseline. Participants who had bariatric surgery during the study period will be only be included at time-points prior to their bariatric surgery. They will be excluded from time-points after their bariatric surgery.

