4.4 Multiple Testing

No corrections will be made for multiple testing. However, due to the large amount of secondary outcomes, statistical models will only be fitted for the most important secondary outcomes to limit the impact of multiple testing. Descriptive summaries will be produced for the other secondary outcomes without multiple testing, as described below.

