5.5 Secondary Outcome Analyses

5.5.1 Primary Analysis of Secondary Outcomes

Secondary anthropometric outcomes will be analysed in a similar way to the primary analysis. These outcomes will be summarised overall and by treatment group.

Categorial outcomes will be summarised using count and percentage. Continuous outcomes will be summarised using mean, standard deviation, median, range, and interquartile range. Binary anthropometric outcomes will be compared between the two treatment arms using logistic regression models with the anthropometric outcome as the outcome and randomisation group and the stratification factors (site, baseline BMI) as covariates. The adjusted odds ratio will be presented along with 95% confidence interval and p-value comparing the two treatment arms. Continuous anthropometric outcomes will be compared using linear regression models with the anthropometric outcome as the outcome and randomisation group and the stratification factors (site, BMI) as covariates. The adjusted mean difference will be estimated along with 95% confidence interval and p-value comparing the two treatment arms. If continuous outcomes are non-normally distributed then they will be transformed or a more suitable regression model will be selected.

No formal statistical testing will take place for the other secondary outcomes due to the large amount of secondary outcomes and to reduce multiple testing. Instead, descriptive analyses will be performed to explore potential patterns in improvements. This will apply to the outcomes relating to obesity-related co-morbidities, referrals to Tier 4 services, treatment satisfaction, treatment compliance, and physical activity. Categorial outcomes will be summarised using count and percentage. Continuous outcomes will be summarised using mean, standard deviation, median, range, and interquartile range. Where it makes sense to do so, for continuous variables the baseline, follow-up, and change values will all be summarised; some outcomes can only be defined at follow-up and so this will not apply to those outcomes.

In all analyses, participants will be analysed in the group to which they were randomised at baseline. Only the complete cases population will be used for the secondary outcomes to reduce the number of models being fitted. Participants who have undergone bariatric surgery during the period of the study will be excluded from these analyses if their bariatric surgery took place before the analysed time-point.

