16.8 Analysis of secondary categorical anthropometric outcomes

Outcome	Control			Intervention			Adjusted difference between the two groups ^a	P-value
	N with data	N with outcome	% with outcome	N with data	N with outcome	% with outcome		
Weight loss of $\geq 5\%$								
16 weeks								
32 weeks								
52 weeks								
104 weeks								
Weight loss of $\geq 10\%$								
16 weeks								
32 weeks								
52 weeks								
104 weeks								
Weight loss of $\geq 15\%$								
16 weeks								
32 weeks								
52 weeks ^b								
104 weeks								
Maintenance of weight loss of $\geq 15\%$ among those								

Outcome	Control			Intervention			Adjusted difference between the two groups ^a	P-value
	N with data	N with outcome	% with outcome	N with data	N with outcome	% with outcome		
who lost $\geq 15\%$ at 52 weeks								
104 weeks								

Abbreviations: CI, Confidence Interval; OR, Odds Ratio.

^a Estimates are adjusted for the stratification variables: site and baseline body mass index ($\geq 45\text{kg}/\text{m}^2$; $< 45\text{kg}/\text{m}^2$).

^b Primary analysis.

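### Week-104 maintenance is given a seven-parameter adjusted logistic model and a p-value, although about 5 controls and 31 intervention participants are expected and the contrast is not protected by randomisation

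*SAP*

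**What the plan says.** SAP 2.2.1 places this among the anthropometric endpoints, at 104 weeks only: "Maintenance of weight loss of $\geq 15\%$ among those who lost $\geq 15\%$ at 52 weeks". It is derived only for participants who had reached the threshold at week 52. It carries secondary objective 3 and aim (b) of Protocol section 4.

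SAP 5.5.1 sets the method: "Binary anthropometric outcomes will be compared between the two treatment arms using logistic regression models". The covariates are randomised group, site and dichotomised baseline BMI, and the output is an adjusted odds ratio, 95% confidence interval and p-value. The template in SAP 16.8, "Analysis of secondary categorical anthropometric outcomes", has a maintenance row under those columns.

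The analysis set is restricted: "Only the complete cases population will be used for the secondary outcomes to reduce the number of models being fitted". For participants who have bariatric surgery, SAP 3.3.1 adds: "They will be excluded from time-points after their bariatric surgery".

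The only model fallback in SAP 5.5.1 concerns continuous outcomes: "If continuous outcomes are non-normally distributed then they will be transformed or a more suitable regression model will be selected". SAP 5.5.3 plans no sensitivity analyses of secondary outcomes. Neither document has a rule for small cells, separation or non-convergence.

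Protocol 11.2 and SAP 1.2.4 estimate 40 intervention participants for the responder analyses. They give no count of control participants expected to reach 15% loss.

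**The concern.** There are two separate problems.

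- **Sparseness.** A model with seven parameters is to be fitted to a subset in which the control arm may hold about five people. If every control has the same outcome, or if there are no controls, the treatment odds ratio has no finite maximum-likelihood estimate. The SAP does not say what would then be reported.
- **Selection.** Membership of each subset depends on week-52 response, which the primary hypothesis (SAP 2.1.2) expects treatment to change. Control achievers and intervention achievers may therefore differ in ways that randomisation does not balance. SAP 4.1 keeps participants in their randomised group, but that does not restore comparability after this selection. A penalised or exact method would address the first problem and not the second.

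At stake is how objective 3 is reported: an adjusted odds ratio with a p-value invites reading as a randomised answer on maintenance.

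**Working it through.** **Inputs (Protocol 11.2, SAP 1.2.4).** Week-52 rates of ≥15% loss are 5% in control (likely range 3-5%) and 16% in intervention (likely range 14-20%). The plan has 131 and 261 randomised, 25% dropout, two-sided 5% alpha and 80% power. There are five sites (SAP 1.2.1) and a binary BMI stratum (SAP 4.3).

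**The plan's own figure.** The standard two-proportion formula (pooled variance under the null, no continuity correction, 2:1) gives 96 controls and 288 in total. Then 288 / 0.75 = 384, within 3% of the stated 392. Power at 98 v 196 evaluable is 81.2%. The inputs are therefore being read as the plan intends.

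**Parameters.** Intercept 1 + arm 1 + site 4 + BMI 1 = 7.

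**Expected week-52 achievers (arm size × 0.75 × rate).**

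- Control: 131 × 0.75 × 0.05 = 4.9. At 3%: 2.9.
- Intervention: 261 × 0.75 × 0.16 = 31.3. At 14-20%: 27.4-39.2.
- No dropout: 131 × 0.05 = 6.6 and 261 × 0.16 = 41.8. The printed 40 is close to this undiscounted figure.

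The endpoint also needs a week-104 weight, so these are upper expectations. The documents give no second-year loss rate. An assumed further 10-25% loss gives 4.4 v 28.2 down to 3.7 v 23.5.

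**Chance of three or fewer control achievers.** Binomial with n = 98: 27% at a 5% rate and 66% at 3%. With an assumed further 10-25% loss at the 5% rate: 35-50%.

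**Chance that the control arm alone makes the odds ratio non-finite.** Let m be the control maintenance rate (assumed) and k the number of control achievers. The probability is the sum over k of Bin(k; 98, 0.05) × [m^k + (1 − m)^k], with the k = 0 term counted once.

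| m | 98 evaluable | 131 (no dropout) |
|---|---|---|
| 30% | 25% | 15% |
| 40% | 18% | 9% |
| 50% | 16% | 7% |

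**Simulation of the planned model.** This is illustrative: 4,000 trials per scenario, five equal sites and 40% in the upper BMI stratum, all assumed. The share with no finite treatment odds ratio at week-52 counts was:

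| Maintenance, control / intervention | Share |
|---|---|
| 50% / 50% | 18% |
| 50% / 70% | 20% |
| 40% / 70% | 25% |
| 30% / 50% | 26% |
| 30% / 70% | 32% |

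With a further 10% loss the range is 24-38%, and with 25% loss 37-50%. With unequal sites (40/20/20/10/10%) and 20% in the upper stratum, week-52 counts give 21-33%.

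**Precision and power.** The exact 95% interval for 2 of 5 controls is 5% to 85%. Fisher power at 5 v 31 depends on the assumed rates: 12% for 50% v 70%, 22% for 40% v 70%, 37% for 30% v 70% and 75% for 20% v 80%.

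**Repeat under SAP 5.5.2.** The responder analysis restricts the intervention arm to week-52 achievers and admits all controls. The maintenance endpoint exists only for achievers in either arm, so the repeat uses the same patients.

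**The planned week-104 comparison.** ≥15% loss at week 104 by randomised arm is already in Table 16.8. If maintenance were identical in both arms at 50-80%, with no new achievers and no further loss, a Fisher test at 98 v 196 would still be significant in 42-69% of trials, because the week-52 difference carries over.

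**The case against.** The other side has several fair points.

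- **The reader is partly protected.** Table 16.8 prints the denominators, counts and percentages for each arm, the SAP requires a confidence interval, and the endpoint's title states the restriction. A control arm of five would be visible. This stands, but it supplies neither a fallback rule nor a statement that the contrast is not randomised.
- **The objective is to compare.** SAP 4.4 says "statistical models will only be fitted for the most important secondary outcomes to limit the impact of multiple testing", and maintenance is a named objective. Removing every test is partly a matter of preference. This stands, so the fix leaves room for a pre-specified exact comparison.

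A reader might also infer more than the documents support:

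- *That the odds ratio will usually be inestimable.* At week-52 counts the simulated rate is 18-32%, so most trials would yield a finite estimate. Higher figures need a second-year loss that the documents do not give. Separation anywhere in the model, including site terms, is commoner but is not the same event.
- *That any test would be powerless.* Fisher power runs from 12% to 75% over the pairs above, and the documents give no maintenance rate.
- *That bariatric surgery will thin this subset.* SAP 5.8 expects surgical participants to be poor responders, so surgery is weak support for shrinkage among week-52 achievers. Missing week-104 weights are the sound reason.
- *That the primary result is at risk.* It is not; this is one row of a secondary table.

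**Conclusion.** The concern holds for the maintenance row. The planned seven-parameter model does not suit about 5 v 31 participants, no rule covers a sparse binary outcome, and the comparison is conditioned on a post-randomisation response.

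The expected counts, the 27% (or 66%) chance of three or fewer controls, the missing rule and the selection argument all rest on the documents' own inputs and text. The 18-32% non-finite rate is illustrative and depends on assumed maintenance rates, site split and BMI split. The sparseness does not depend on those assumptions, since even with no dropout only about 6.6 controls are expected. The point is worth settling before the SAP is signed off, and it goes no further than this endpoint.

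**What to change.** For the maintenance row only:

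1. In SAP 5.5.1 and Table 16.8, replace the adjusted logistic model with n/N and an exact 95% confidence interval per arm. Label the row descriptive, selected on week-52 response, and not a randomised comparison.
2. If the sponsor wants a formal comparison for secondary objective 3, pre-specify an unadjusted exact method in place of the seven-parameter model, with the same label.
3. State that the row is not repeated under SAP 5.5.2, because the patients are the same.
4. Record the change in SAP 5.8 as a departure from Protocol 11.1. Tabulation without a model is already the SAP's route for other secondary outcomes.
5. For between-arm evidence at week 104, point to the planned comparison of ≥15% loss by randomised arm. Note beside it that it uses complete cases, that it excludes participants after surgery (Protocol 6.2 says "more participants in the control group are expected to have bariatric surgery than in the targeted prescribing pathway treatment group"), and that it carries over the week-52 effect. It therefore does not measure maintenance as such.

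The cost is SAP wording, with no new data or endpoint. The downside is that the adjusted test of maintenance is lost. What that gives up depends on maintenance rates that the documents do not state.
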